9.3.3 Study Endpoints

1. Safety

- Death
- Organ transplantations

- Hospitalisations
 - CF complications including but not limited to hepatobiliary, gastrointestinal, and pulmonary conditions
 - Pulmonary exacerbations and respiratory microbiology
 - Serious safety outcomes
2. Pregnancy
 - Live birth
 - Stillbirth
 - Spontaneous abortion
 - Therapeutic abortion
 - Gestational age
 - Congenital anomalies
 3. Drug utilisation
 - Ivacaftor exposure in patients with CF
 4. CF disease progression
 - CF lung disease severity based on percent predicted FEV₁
 - Clinical signs of CF disease progression
 - Change in lung function over time

9.3.4 Statistical Analyses

Data analyses will be performed by the CF Trust and CF Foundation to meet the study objectives. The results of the annual analyses will be reported in the study report.

The primary objectives of this study are to evaluate long-term safety, pregnancy outcomes, drug utilisation, and CF disease progression in patients treated with ivacaftor. Descriptive statistics will be calculated for all endpoints. All safety, pregnancy, and CF disease progression endpoints will be compared between the Ivacaftor and Comparator Cohorts or between the Ivacaftor Pregnancy and Comparator Pregnancy Cohorts. Safety and pregnancy outcomes will also be described for the Historical Cohort. Annual incidence rates will be calculated for safety outcomes (Objective 1). Crude relative risks or risk difference with 95% confidence intervals will be calculated for some outcomes, as appropriate. Statistical modelling with adjustment for confounders and effect modifiers will be conducted, as possible, due to the likely sparse data. Identification of confounders and effect modifiers will be performed using stratified analyses. Each annual report will include the patient data from the previous calendar year (e.g., annual cross-sectional analysis). Longitudinal analyses will be included, as appropriate, in the final report.

This section presents a summary of the planned statistical analyses for this study (see [Stand-alone Document 4](#) listed in Annex 1. List of Stand-alone Documents). A detailed

analysis plan will be presented in a statistical analysis plan. A summary of the comparisons to be made for each objective is provided in Table 5.

Table 5 Comparisons by Primary Objective

Objective	Setting	Cohorts Included	Comparisons
1. To evaluate the long-term safety of ivacaftor in patients with CF	UK, US	Ivacaftor; Comparator; Historical	
 Comparison of long-term safety between the Ivacaftor Cohort (ivacaftor-treated patients) and the Comparator Cohort (concurrent nonexposed patients) to include relative risks or risk differences Descriptive statistics for the Historical Cohort (historical nonexposed patients) will be available for comparison to the Ivacaftor Cohort (ivacaftor-treated patients). Comparisons to be based on 95% confidence intervals.
2. To evaluate the outcomes of pregnancy in ivacaftor-treated patients	UK, US	Ivacaftor Pregnancy Study; Comparator Pregnancy Study; Historical	
 Comparison of pregnancy outcomes between the Ivacaftor Pregnancy Study Cohort (ivacaftor-treated patients) and the Comparator Pregnancy Study Cohort (concurrent nonexposed patients) Descriptive statistics for the Historical Cohort (historical nonexposed patients) will be available for comparison to the Ivacaftor Pregnancy Study Cohort (ivacaftor-treated patients). Comparisons to be based on 95% confidence intervals.
3. To evaluate the drug utilisation of ivacaftor	UK, US	Drug Utilisation	All ivacaftor-treated patients will be included in the drug utilisation analysis. No comparisons will be made.
4. To evaluate CF disease progression in ivacaftor-treated patients	UK, US	Ivacaftor Comparator	
 Comparison of CF disease progression between the Ivacaftor Cohort (ivacaftor-treated patients) and the Comparator Cohort (concurrent nonexposed patients)

CF: cystic fibrosis; UK: United Kingdom; US: United States.

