9.1.1 Study Population

The Ivacaftor Cohort will include all patients who have been treated with ivacaftor and are enrolled in the CF Trust or CF Foundation patient registries. The Comparator Cohort will include patients who have never been exposed to ivacaftor and are matched on age group, *CFTR* genotype class, and sex (see Section 9.2.4) to patients in the Ivacaftor Cohort.

The Ivacaftor Pregnancy Study Cohort will include all female patients who have ivacaftor exposure in the analysis year and are enrolled in the CF Trust or CF Foundation patient registries. The Comparator Pregnancy Study Cohort will include female patients who have never been exposed to ivacaftor and are matched on *CFTR* genotype class to patients in the Ivacaftor Pregnancy Study Cohort (see Section 9.2.4).

The Comparator and Comparator Pregnancy Study Cohorts will be identified for each registry's Ivacaftor and Ivacaftor Pregnancy Study Cohorts, respectively, at a ratio of m:1, where m is the maximum number of matches available.

The Historical Cohort will include patients who have the *G551D-CFTR* mutation, were enrolled in the patient registries before ivacaftor was available in clinical studies and commercially in the US and the UK (i.e., 2008), and were never exposed to ivacaftor.

The Drug Utilisation Cohort will include all patients who have ever been treated with ivacaftor.

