9.1.2.5 Comparator Pregnancy Study Cohort

Inclusion Criteria

1. Female patients with CF in the CF Trust or the CF Foundation patient registries
2. Patients 13 years of age or older
3. Patients with no evidence of ivacaftor exposure (current or past)
4. Patients matched on *CFTR* genotype class to patients in the Ivacaftor Pregnancy Study Cohort

Exclusion Criterion

1. Participation in an interventional study during the analysis period (if available)

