9.2.4 Comparator Matching

For analyses of safety outcomes and CF disease progression (Objectives 1 and 4), patients in the Comparator Cohort will be matched to patients in the Ivacaftor Cohort on age group, then *CFTR* genotype class, and then, whenever possible, sex, to account for differences in health outcomes during the progression of CF and known differences in health outcomes for male and female patients.²³⁻²⁷

For analyses of pregnancy outcomes (Objective 2), patients in the Comparator Pregnancy Study Cohort (female patients only) will be matched to patients in the Ivacaftor Pregnancy Study Cohort on *CFTR* genotype class; no other matching criterion is used in order to maximise the number of potential matches for an event (pregnancy) expected to have low incidence compared to other safety outcomes.

Age

Age matches will be made based on an age bracket within specific age group categories.

- Patients 0 to 11 years of age (inclusive) will have a bracket of ± 2 years.
- Patients 12 to 20 years of age (inclusive) will have a bracket of ± 2 years.
- Patients older than 20 years of age will have a bracket of ± 5 years.
- Age group categories will be 0 to 2, 3 to 5, 6 to 8, 9 to 12, 13 to 17, 18 to 20, 21 to 25, 26 to 30, 31 to 35, 36 to 40, and >40 years.

For example, a 16-year-old Ivacaftor Cohort patient will be matched to patients in the Comparator Cohort within the bracket of ± 2 years of age (i.e., 14 to 18 years of age), as

limited by the age group category of 13 to 17 years of age (i.e., final age match to patients 14 to 17 years of age). A 21-year-old Ivacaftor Cohort patient will be matched to patients in the Comparator Cohort within the bracket of ± 5 years of age (i.e., 16 to 26 years of age), as limited by the age group category of 21 to 25 years of age (i.e., final age match to patients 21 to 25 years of age).

Age group categories may be collapsed to increase matching when nonexposed patients are not available for matching. These age groups were chosen based on the age-related decline in pulmonary function in patients with CF.^{28,29}

CFTR genotype class

[figure not shown]

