9.9 Limitations of the Research Methods

Limitations of missing data

Missing data may introduce misclassification of exposure and outcomes in observational studies. The CF Trust and CF Foundation patient registries have robust systems in place to minimise missing data in their patient registry databases. These procedures are described in the data management and quality control sections (Sections 9.6 and 9.8). For the CF Trust, data completeness is assessed each year. Of patients known to be alive, 89% have evidence of at least an annual encounter in the CF Trust Patient Registry database. Amongst patients with at least an annual encounter visit, 95% have evidence of pulmonary function measure (e.g., FEV₁). For the CF Foundation, data completeness in the CF Foundation Patient Registry is stimulated by associating the amount of annual grant awards to the CF centres to the quality of data entered. As a result, 94% of patients' records in 2011 had medications data, 91% had complications data, and 91% had microbiology data. Additionally, 96% of CF nontransplant patients 6 years or older and known to be alive had recorded pulmonary function test measurements. Whilst missing data are minimised in the patient registries, exploratory and sensitivity analyses will be employed to understand the impact of missing data on the primary objectives of the study.

Limitations of observational studies

The nature of observational studies with nonrandom treatment assignment allows for the concern of selection bias. The concern is that patients treated with ivacaftor could be systematically different and have different risk factors for adverse events than patients who choose other treatments or are not eligible for ivacaftor. The design strategy of this study is a matched-comparator cohort (patients who have not been exposed to ivacaftor). Selection bias will be minimised by matching on age group, *CFTR* genotype class, and sex, as appropriate. Other variables that may influence selection bias, such as pancreatic sufficiency status or diabetes status, will be assessed as confounders in the statistical analyses through stratification and adjustment, when possible.

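### Comparators are taken at m:1 without saying whether m is constant, and the only effect measure specified is crude; if m varies with age, genotype class or sex, the matched balance can be lost

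*Protocol*

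**What the plan says.** **Design.** Section 9.1.1 (and Study Size in the Section 4 abstract) sets the comparator cohorts for each registry "at a ratio of m:1, where m is the maximum number of matches available". Nothing says whether m is constant. For safety and disease progression, Section 9.2.4 has comparators "matched to patients in the Ivacaftor Cohort on age group, then *CFTR* genotype class, and then, whenever possible, sex". It also allows loosening: "Age group categories may be collapsed to increase matching when nonexposed patients are not available for matching". For pregnancy, Section 9.2.4 matches on genotype class alone and gives the reason, which is to keep as many matches as possible for a rare event. The only age limit there is a shared lower one: "Patients 13 years of age or older" (Section 9.1.2.5).

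**Analysis.** Section 9.3.4 says: "Crude relative risks or risk difference with 95% confidence intervals will be calculated for some outcomes, as appropriate". It goes on: "Statistical modelling with adjustment for confounders and effect modifiers will be conducted, as possible, due to the likely sparse data". The abstract is weaker and says such modelling may not be possible. Section 9.3.4.1 stratifies every safety outcome by age, sex and genotype class, among other variables. Section 9.3.4 gives the purpose of stratified analysis as finding confounders and effect modifiers. Section 9.3.4.2 describes pregnancies by age. Table 5 names relative risks or risk differences for Objective 1 only, and bases the Objective 2 comparisons on 95% confidence intervals.

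**Reliance.** Section 9.9 states: "Selection bias will be minimised by matching on age group", genotype class and sex. Other variables are left to stratification and adjustment when possible.

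**The concern.** Matching in a cohort balances the matching factors in a crude comparison only if each exposed patient brings the same number of comparators, or if the factors do not affect the outcome. The protocol itself treats age and sex as prognostic, since that is its stated reason for matching on them. If well-supplied strata bring many comparators and scarce strata bring few, the pooled comparators take on the mix of the available pool. A crude relative risk then carries confounding by the factors that were matched on.

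At stake is the between-cohort summary for death, transplantation, hospitalisation and the other safety outcomes. The distortion can go either way, so in a safety study it could suggest a harm that is not there or hide one that is.

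For pregnancy, age is neither matched nor fixed as an adjustment, although pregnancy frequency can be expected to depend on age.

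**Working it through.** **1. The plan's own figure.** Table 6 (Section 9.5) gives power for an unexposed death rate of 0.011 (103/9385), using a one-sided Fisher exact test at alpha 0.1 with equal group sizes. Exact enumeration agrees with all 24 cells within 0.007. At a relative risk of 2, for example, it gives 0.386 and 0.706 against the stated 0.393 and 0.703 (N = 432 and 1035). The table assumes 1:1, so it is silent on m.

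**2. Average m.** Section 7.1 says more than 88% of US patients carry *F508del*, about half of them homozygous. Section 9.2.1 gives about 26,000 US registry patients, and Section 9.5 gives 1035 with *G551D*. So 0.88 × 0.5 × 26,000 = 11,440, and 11,440 / 1035 ≈ 11 comparators per exposed patient before age and sex limits. This is an average and does not show how m is spread.

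**3. Age mix, no drug effect.** *Assumed:* annual death risk 0.2% under 18 and 2% in adults; comparator pool 45% adult.

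Comparator risk = 0.45 × 0.02 + 0.55 × 0.002 = 0.0101.

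| Ivacaftor Cohort adult | Its risk | Crude RR | Implied m, adult relative to child |
|---|---|---|---|
| 50% | 0.0110 | 1.09 | (0.45/0.5)/(0.55/0.5) = 0.82 |
| 60% | 0.0128 | 1.27 | (0.45/0.6)/(0.55/0.4) = 0.55 |
| 70% | 0.0146 | 1.45 | (0.45/0.7)/(0.55/0.3) = 0.35 |

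**4. Varying m directly.** *Assumed:* two exposed strata of equal size, overall exposed risk 0.011, no drug effect. With older/younger risk ratio k, the younger risk is r = 0.022/(1 + k) and the older risk is kr.

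Crude RR = 0.011 / [(m_young × r + m_old × kr) / (m_young + m_old)].

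Example: k = 10, m = 10 and 2 gives r = 0.002, comparator risk (0.02 + 0.04)/12 = 0.005, and RR 2.20.

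| k | m 5, 5 | m 6, 4 | m 10, 5 | m 10, 2 | m 2, 10 |
|---|---|---|---|---|---|
| 1 | 1.00 | 1.00 | 1.00 | 1.00 | 1.00 |
| 2 | 1.00 | 1.07 | 1.13 | 1.29 | 0.82 |
| 5 | 1.00 | 1.15 | 1.29 | 1.80 | 0.69 |
| 10 | 1.00 | 1.20 | 1.38 | 2.20 | 0.65 |

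(m is given as younger, older.) Within each stratum the two cohorts have the same risk, so the Mantel-Haenszel RR and the 1/m-weighted RR are 1.00 in every cell.

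**5. Pregnancy frequency, no drug effect.** *Assumed:* yearly rates of 1%, 6% and 1% at ages 13–17, 18–34 and 35 or over; ivacaftor mix 25/60/15%.

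Ivacaftor rate = 0.25 × 0.01 + 0.60 × 0.06 + 0.15 × 0.01 = 0.040.

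- 40% of comparators aged 18–34: 0.40 × 0.06 + 0.60 × 0.01 = 0.030, ratio 1.33.
- 65% of comparators aged 18–34: 0.65 × 0.06 + 0.35 × 0.01 = 0.0425, ratio 0.94.

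**The case against.** The strongest reply is that a varying m is an inference. The ratio is set for each registry's cohort and can be read as one m per registry. A crude ratio then keeps the balance on whatever was matched. That stands: a reader might infer that the matching is certainly undone, and the text does not support this. Against the fixed reading, Section 9.2.4 expects some strata to run short of comparators, and a single m would be held down by the scarcest set, which fits poorly with taking the maximum. The protocol has to say which applies.

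A reader might also infer that a crude relative risk is the sole or headline estimate. It is not. Crude measures are for some outcomes, every safety outcome is stratified by the three matching factors, and adjusted modelling is planned where possible. These are real mitigations. They do not name a pooled estimate that uses the strata, and modelling is the part that sparse data may remove.

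A third reply is that the choice of estimator belongs in the SAP. Much of the detail does, but the protocol itself specifies the crude measure, so this is a comment on a stated method.

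On pregnancy, a reader might see the missing age match as an oversight. It is a deliberate trade-off with its reason given, and Table 5 assigns no relative risk or risk difference to Objective 2. What remains is that no age adjustment is fixed. Stratifying or standardising loses no matches, so the stated reason does not argue against it.

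Finally, the study is descriptive and hypothesis-generating (Section 8.3), which lowers the stakes without removing them.

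**Conclusion.** The point holds conditionally. If m is constant across matched sets, the crude estimate keeps the balance. If m varies with age, genotype class or sex, it can lose it, and the protocol fixes no summary that would restore it.

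Under the assumed age mixes the crude ratio with no effect is 1.09 to 1.45. Over the wider assumed grid it runs from 0.65 to 2.20. Only the extreme corner, a tenfold risk gradient with 10 against 2 comparators, reaches the 2- to 3-fold differences that Section 9.9 says the study can detect. The documents give no risks by age, no age distributions and no spread of m, so neither the size nor the direction of any bias can be taken from them.

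For pregnancy, only the lack of a fixed age adjustment stands. The 0.94 to 1.33 range concerns frequency, a secondary objective, and also rests on assumed rates and mixes. This is a worthwhile, inexpensive correction; the documents do not show that the planned comparisons are invalid.

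**What to change.** In Section 9.3.4:

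- State whether m is fixed or variable.
- If variable, keep all matches but replace the crude summary by a Mantel-Haenszel relative risk or risk difference stratified by age category × genotype class × sex. Alternatively, weight each comparator 1/m within its set, summing the weights and using a patient-level robust variance if comparators are reused. Weighting restores only what the sets were matched on, so where sex was not matched or age categories were collapsed, the stratified form is the safer one.
- Bring Section 4 and Section 9.3.4 into agreement on whether adjusted modelling will be done.

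For Objective 2, keep the genotype-only match, and stratify the comparison of pregnancy frequency and outcomes by age category, or standardise it to age, where numbers allow.

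The cost is about a paragraph of text, a little more registry programming and slightly wider intervals. No data are lost to matching, although strata without comparators will not contribute to a Mantel-Haenszel estimate.

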6 MILESTONES

Based on the marketing authorisation dates of ivacaftor in the United States (US; 31 January 2012) and European Union (EU; 23 July 2012), the milestones for data collection and analysis are different for the 2 patient registries, as indicated in the table below. Ivacaftor was first made commercially available in the US in February 2012. Ivacaftor has been commercially available (reimbursed) in the United Kingdom (UK) since January 2013. Each year, the Cystic Fibrosis (CF) Trust and CF Foundation create a data set for the patient registries. The process includes a data lock point of 31 December (US) and 31 January (UK) followed by a 3- to 4-month data entry and data cleaning period when sites are queried for data discrepancies. The final data made available to Vertex by the registries in April/May (US) and June (UK) each year will comprise patient data from the previous calendar year. Vertex's summary of the data provided and the preparation and submission of an annual study report are expected to be a 5- to 6-month process.

The milestones provided are based on protocol finalisation by June 2013.

Table 1 Study Milestones

Milestone	Planned Date	
	CF Trust (UK)	CF Foundation (US)
Start of data collection ^a	June 2013 ^b	June 2013 ^b
End of data collection ^a	June 2017	May 2017
Year 1 Report	December 2013 ^c	December 2013 ^c
Year 2 Report	December 2014	October 2014
Year 3 Report	December 2015	October 2015
Year 4 Report	December 2016	October 2016
Registration in EU PAS Register ^d	tbd	tbd
Final report of study results	December 2017	October 2017

CF: cystic fibrosis; EU PAS: European Union Post-authorisation Study; tbd: to be determined; UK: United Kingdom; US: United States.

^a Per EU Good Pharmacovigilance Practices VIII.B.2, the start and end of data collection for secondary use of data are when the analytical datasets are available.

^b Data for the Historical Cohort will have been collected by the registries before ivacaftor was commercially available in the respective regions. The data extraction for the Historical Cohort will be conducted as part of the Year 1 Report activities.

^c Based on the protocol finalisation date, the Year 1 Report will be completed later in the year than later annual reports (i.e., December instead of October).

^d Study will be registered in EU PAS Register following Pharmacovigilance Risk Assessment Committee approval of final protocol and before study initiation.

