9.2.5 Other Matching Considerations

Given the limited size of the CF population, the Comparator and Comparator Pregnancy Cohorts will not be matched for other measures of disease severity (e.g., percent predicted FEV₁, *Pseudomonas aeruginosa* infection) due to concerns about availability of adequate patients for matching. However, measures of disease severity will be included as stratification variables and as covariates for adjustment, as necessary.

The Historical Cohort will include patients with a *G551D-CFTR* mutation who were in the patient registries in 2008. These patients were chosen because they represent the best match to ivacaftor-treated patients in 2012 and later because they match the indicated patient population based on the approved product labelling. The Historical Cohort will include patients of all ages and will be stratified to identify outcomes for patients younger than 6 years of age (for the potential off-label population). The year 2008 was chosen because starting in 2009, ivacaftor clinical studies were actively enrolling in the UK and US. A 1-year window was selected to match the window for safety outcome analysis in the Ivacaftor and Comparator Cohorts. The Historical Cohort will be analysed once for Objectives 1 and 2 for all stratification variables. If additional analyses are identified during the conduct of the study, the Historical Cohort will be available for analysis.

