9.3.1.2 Outcomes

Death will be defined if there is evidence of a date of death in the database. Cause of death will include respiratory/cardiorespiratory, liver disease, trauma, suicide, transplant-related, and other.

Organ transplantations will be defined if there is evidence of an organ transplantation. Type of transplant will include lung and other.

Hospitalisations will be defined if there is evidence of a start date for a hospitalisation for a pulmonary exacerbation.

CF complications include the following:

- allergic bronchial pulmonary aspergillosis (ABPA)
- absence of vas deferens
- arthritis
- arthropathy
- asthma
- bone fracture
- cancer confirmed by histology
- cardiac disease
- CFRD
- chronic *P aeruginosa* colonisation
- chronic *Staphylococcus aureus* colonisation
- cirrhosis with portal hypertension
- cirrhosis with no portal hypertension
- depression
- DIOS
- fibrosing colonopathy/colonic stricture
- gallbladder disease requiring surgery
- gastroesophageal reflux disease (GERD)
- gastrointestinal (GI) bleed (non-variceal) requiring hospitalisation
- GI bleed (variceal) requiring hospitalisation
- Haemoptysis
- Hearing loss
- hypertension
- kidney stones
- liver disease, non-cirrhosis
- liver enzymes elevated
- nasal polyps requiring surgery
- nontuberculous mycobacteria (NTM) infection (not requiring treatment)
- NTM infection (requiring treatment)
- osteopenia
- osteoporosis
- pancreatitis
- peptic ulcer disease
- pneumothorax requiring chest tube
- port inserted or replaced
- rectal prolapse
- renal failure requiring dialysis
- septicaemia
- sinus disease
- other, specify including cataract

Pulmonary exacerbations will be defined by evidence of a CF care episode or hospitalisation with reason pulmonary exacerbation. Respiratory microbiology will include patients with a bacterial culture and evidence of chronic colonisation with *Staphylococcus aureus*, chronic *P aeruginosa*, intermittent *P aeruginosa*, *Burkholderia*, methicillin-resistant *Staphylococcus aureus*, and *Haemophilus influenzae*.

Serious safety outcomes will be defined by combining death, organ transplantations, hospitalisations, and selected CF complications.

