9.3.2 Variables for Cystic Fibrosis Foundation Patient Registry (US)

9.3.2.1 Exposure

Ivacaftor exposure will be determined by first evidence of ivacaftor treatment and patients will remain exposed until there is evidence of discontinuation of ivacaftor in the patient registry database. Because start and stop dates are not available, algorithms will be used to extrapolate duration of exposure based on timing of patient encounters and drug exposure data available. The exposure algorithm includes the following rules: the date of the first encounter with evidence of ivacaftor exposure will be used as the start date. Patients will be identified as exposed to ivacaftor until a medications form is completed where ivacaftor treatment is not reported. The ivacaftor stop date will be the encounter date where exposure is not indicated. Ivacaftor exposure will be categorised into the meaningful groups based on the distribution of exposure, such as <1 year, 1 to <2 years, and ≥2 years.

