9.3.4.1 Safety (Objective 1)

Safety outcomes for the Ivacaftor Cohort and the Comparator Cohort will include 6 main categories: death, organ transplantation, hospitalisations, CF complications, and pulmonary exacerbations and respiratory microbiology, and serious safety outcomes (composite outcome). The safety outcomes will be analysed for the Historical Cohort.

1. Death: Frequency of death will be calculated and will include cause of death and age at death. Analyses will be stratified by duration of ivacaftor exposure, age, sex, *CFTR* genotype class, percent predicted FEV₁, and comorbid conditions.
2. Organ transplantations: Frequency of organ transplantations will be calculated and will include type of organ transplanted and age at transplant. Analyses will be stratified by duration of ivacaftor exposure, age, sex, *CFTR* genotype class, percent predicted FEV₁, and comorbid conditions.

3. Hospitalisations: Frequency of hospitalisations will be calculated and will include the number of days of hospitalisation, and age at hospitalisation. Analyses will be stratified by duration of ivacaftor exposure, age, sex, *CFTR* genotype class, percent predicted FEV₁, and comorbid conditions.
4. CF complications: Frequency of CF complications will be calculated. CF complications include infections, arthritis, asthma, bone fracture, diabetes, and several hepatic, gastrointestinal, and pulmonary complications. Analyses will be stratified by duration of ivacaftor exposure, age, sex, *CFTR* genotype class, percent predicted FEV₁, and comorbid conditions.
5. Pulmonary exacerbations and respiratory microbiology: Frequencies of pulmonary exacerbations and respiratory microorganisms will be calculated. Analyses will be stratified by duration of ivacaftor exposure, age, sex, *CFTR* genotype class, percent predicted FEV₁, and comorbid conditions.
6. Serious safety outcomes: Frequency of serious safety outcomes will be calculated. Analyses will be stratified by duration of ivacaftor exposure, age, sex, *CFTR* genotype class, percent predicted FEV₁, and comorbid conditions.

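### The one-year safety window has no start-of-treatment rule, so first-treated-year comparisons are biased, and chronic complications are counted without separating new from existing disease

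*Protocol*

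**What the plan says.** **Window and measure.** Section 9.2.5 explains the Historical Cohort's length by the window used for the other two cohorts: "A 1-year window was selected to match the window for safety outcome analysis in the Ivacaftor and Comparator Cohorts". Section 9.3.4 applies that window as a calendar year: "Each annual report will include the patient data from the previous calendar year (e.g., annual cross-sectional analysis". It names the measure, "Annual incidence rates will be calculated for safety outcomes (Objective 1", and the contrast, "Crude relative risks or risk difference with 95% confidence intervals will be calculated for some outcomes, as appropriate".

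**Cohort entry.** Section 9.1.2.1 asks only that the patient is in a registry and was treated with ivacaftor. Section 9.9 says eligibility is settled afresh each year.

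**Start of treatment.** Sections 9.3.1.1 (UK) and 9.3.2.1 (US) define exposure from first evidence of treatment. In the US, "the date of the first encounter with evidence of ivacaftor exposure will be used as the start date". The start date is used for duration of exposure, for the duration strata in 9.3.4.1 and for baseline FEV1 (9.3.1.3, 9.3.2.3). It is not used to decide which safety events count.

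**Launch.** Section 6 says "Ivacaftor was first made commercially available in the US in February 2012" and dates UK commercial availability to January 2013. Under Table 2, the first Ivacaftor-versus-Comparator safety comparison uses US 2012 data, and the first UK comparison uses 2013 data.

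**Complications.** Section 9.3.4.1 says "CF complications: Frequency of CF complications will be calculated". The lists in 9.3.1.2 and 9.3.2.2 mix episodic items with chronic ones (CFRD, cirrhosis, osteoporosis, hearing loss) and include "absence of vas deferens". No safety text asks that the condition be new.

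**The concern.** Two separate biases follow from carrying out the plan as written.

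The first is confined to the calendar year in which a patient starts. The patient must survive to a treated record to be in the Ivacaftor Cohort, whereas a comparator is at risk of death all year. That is immortal time, and it favours ivacaftor. Hospitalisations and exacerbations earlier in the same year are charged to ivacaftor although the patient was untreated. This pulls the ratio towards the cohorts' baseline difference, which means towards 1 if baseline risk is equal.

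The second is present in every report. A chronic condition recorded years before treatment counts the same as one that arose on treatment, yet safety results are labelled incidence rates. Section 7.2 names hepatotoxicity and cataracts as concerns that clinical data have not settled. For such conditions the new cases are what matter, and they are diluted by existing ones.

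**Working it through.** **1. The plan's own figure.** Inputs from section 9.5: death proportion 103/9385 = 0.01097, used as 0.011; one-sided Fisher exact test, alpha 0.1; equal groups of 432 (UK) or 1035 (US). Exact enumeration reproduces all 24 power values in Table 6 to within 0.007. At RR 2 it gives 0.386 / 0.706 against the stated 0.393 / 0.703. At RR 3 it gives 0.769 / 0.982 against 0.772 / 0.981. The table is correctly computed but assumes a full year at risk in both groups.

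**2. Deaths in a starting year.** Let f be the mean share of the calendar year after start. With risk constant over the year, observed RR = f × true RR. The protocol gives no f, so it is assumed:

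| Start pattern (assumed) | Mean share before start | f = null death RR |
|---|---|---|
| Even, February to December | (1/12 + 1)/2 = 0.542 | 0.46 |
| Even, February to end of June | (1/12 + 6/12)/2 = 0.292 | 0.71 |
| Mostly very early in the year | 0.10 | 0.90 |

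At f = 0.5 with no effect, expected ivacaftor deaths are 432 × 0.011 × 0.5 = 2.4 and 1035 × 0.011 × 0.5 = 5.7, against 4.8 and 11.4 in comparators. A true RR of 2 then reads 1.0, and power falls from 0.386 / 0.706 to 0.052 / 0.068. At f = 0.75 a true RR of 2 reads 1.5, with power 0.185 / 0.350.

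**3. Repeatable events in a starting year.** With equal baseline risk, observed RR = (1 − f) + f × true RR. At f = 0.458, a true RR of 0.60 reads 0.542 + 0.275 = 0.82, and a true RR of 1.5 reads 0.542 + 0.687 = 1.23.

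**4. Chronic complications in any year.** Let q be the prevalence and i the annual incidence among patients still free of the condition. Then observed ratio = (q + (1 − q)·i·R) / (q + (1 − q)·i). With i = 1% and R = 2 (both assumed):

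- q = 2%: 0.0396 / 0.0298 = 1.33
- q = 10%: 0.118 / 0.109 = 1.08
- q = 20%: 0.216 / 0.208 = 1.04

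**5. After the change.** If both groups are followed from the same date, the expected death RR returns to its true value, but less time is observed. At f = 0.5 power is 0.207 / 0.444 for RR 2 and 0.480 / 0.835 for RR 3.

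**The case against.** **The SAP may settle it.** The protocol never says outright that events before start belong to ivacaftor. Section 9.3.4 calls itself a summary, and at-risk rules are ordinary SAP content. It is true that the counting is inferred. But the protocol itself states the one-year window, the calendar-year cross-section, the yearly cohort assignment and the incidence label, and these together create the bias. A SAP that counted only post-start events would have to narrow the window in 9.2.5 for starters.

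**Other parts of the plan help.** Stratifying by duration of exposure isolates recent starters, though it leaves their pre-start time in. Section 9.9 discusses differential follow-up, but mentions neither immortal time nor existing disease. Section 9.3.4.4 plans yearly status and shifts in state for CFRD and DIOS under Objective 4, so a new CFRD signal has another route to notice. This part of the objection stands.

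**The study is descriptive.** It is, with no prior hypotheses for the primary objectives. It still plans relative risks with confidence intervals, and section 8.3 states expected directions for incidence.

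**Readings that go too far.** A reader might infer that mortality is biased throughout the study, or that 0.46 is the size of the error. The documents support neither. Years treated throughout are unaffected, including those of former clinical-study patients who stay on treatment. With a static US cohort and five equal years (assumed), a launch-year value of 0.458 averages to (0.458 + 4)/5 = 0.89; later starters would lower it somewhat. A reader might also infer that most listed complications are chronic and that a hepatic or lens signal will be hidden. The protocol gives no prevalences, and many listed items are episodic: fracture, pneumothorax needing a chest tube, DIOS, pancreatitis.

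**Conclusion.** The point holds within limits. In a patient's first treated calendar year the plan as written favours ivacaftor on death and charges it with earlier non-fatal events. With no effect, the death RR for such a year reads about f, from 0.46 to 0.9 over the start patterns considered. These values assume constant risk within the year, equal baseline risk and an unstated start pattern. The effect falls mainly on US 2012 and UK 2013, which supply each registry's first comparison, and on later starters.

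Separately, and in every report, counting chronic complications as recorded under an incidence label shrinks a true doubling to between 1.33 and 1.04 at assumed prevalences of 2% to 20%. Episodic complications are much less affected. Table 6 is not wrong, but it does not describe a launch year.

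**What to change.** Amend 9.2.5, 9.3.4 and 9.3.4.1:

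- **First treated year.** Count deaths, dated events (hospitalisations, exacerbations) and person-time only from ivacaftor start. Require matched comparators to be alive at, and followed from, the same calendar date. Report rates per person-year.
- **Chronic complications.** Report new onset among patients without the condition in the prior registry year, and show prevalence separately. Use the same absent-last-year rule for undated annual UK items.
- **Outcome list.** Drop absence of vas deferens from the incidence outcomes.
- **Limitations (9.9).** State that the US start is the first encounter showing exposure, so some early on-drug events are missed. State also that launch-year event counts and power fall below Table 6.

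The cost is wording and programming. Death dates, hospitalisation start dates (in the UK, for exacerbation admissions only), start dates or a rule to derive them, and prior-year records are already in the registries. Date-matching of comparators is already planned for baseline FEV1. The price is fewer counted events in starting years, as the power figures at f = 0.5 show.
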